**Table 1. Schedule of Visits and Clinical Parameters- LAL Group**

Visits	Preop (Bilateral)	Operative Primary Eye	Postop Day 1 Primary Eye	Postop Week 1 Primary Eye	Operative Fellow Eye	Postop Day 1 Fellow Eye	Postop Week 1 Fellow Eye	Postop Week 3 [REDACTED] Treatment (Bilateral)	Adjustment #1 (Bilateral)	Adjustment #2 (Bilateral)	Adjustment #3 (if needed) (Bilateral)	Lock-in #1 Primary Eye	Lock-in #2 Primary Eye, if needed	Lock-in #1 Fellow Eye	Lock-in #2 Fellow Eye, if needed	Postop Month 3 (Bilateral)	Postop Month 6 (Bilateral)	Postop Month 12 (if needed)	Unscheduled Visit 
Monocular photopic uncorrected distance visual acuity using a +0.25 D lens to compensate for 4 meter test distance	X		X	X		X	X	X	X	X	X	X	X	X	X	M	X	X	
Binocular photopic uncorrected distance visual acuity using a +0.25 D lens over each eye to compensate for 4 meter test distance																M			
Manifest Refraction	X			X		X	X	X	X	X	X	X	X	X	X	X	M	X	
Monocular photopic best corrected distance visual acuity	X			X		X	X	X	X	X	X	X	X	X	X	M	X	X	
Monocular photopic uncorrected distance visual acuity (no trial lens in front of eye)	X			X		X	X	X	X	X	X	X	X	X	X	M		X	
Ocular Dominance	X						X										M		
Undilated pupil diameter	[REDACTED]															M			
Depth of focus testing																M			
Monocular mesopic distance corrected intermediate visual acuity																M			

Visits	Preop (Bilateral)	Operative Primary Eye	Postop Day 1 Primary Eye	Postop Week 1 Primary Eye	Operative Fellow Eye	Postop Day 1 Fellow Eye	Postop Week 1 Fellow Eye	Postop Week 3 [REDACTED] Treatment (Bilateral)	Adjustment #1 (Bilateral)	Adjustment #2 (Bilateral)	Adjustment #3 (if needed) (Bilateral)	Lock-in #1 Primary Eye	Lock-in #2 Primary Eye, if needed	Lock-in #1 Fellow Eye	Lock-in #2 Fellow Eye, if needed	Postop Month 3 (Bilateral)	Postop Month 6 (Bilateral)	Postop Month 12 (if needed)	Unscheduled Visit 
Monocular mesopic best corrected intermediate visual acuity																	M		
Monocular mesopic best corrected near visual acuity																	M		
Monocular mesopic distance corrected near visual acuity																	M		
Monocular photopic distance corrected near visual acuity																	X	M	
Monocular photopic uncorrected near visual acuity																	X	M	
Binocular photopic uncorrected near visual acuity																	M		
Binocular photopic uncorrected intermediate visual acuity																	M		
Monocular photopic uncorrected intermediate visual acuity																	X	M	
Monocular photopic distance corrected intermediate visual acuity																	X	M	
[REDACTED]								X	X	X	X	X	X	X 	X	X	M	X	X
[REDACTED]								X	X	X	X	X	X	X 	X	X	M	X	X
Mesopic undilated pupil diameter																	M		

Visits	Preop (Bilateral)	Operative Primary Eye	Postop Day 1 Primary Eye	Postop Week 1 Primary Eye	Operative Fellow Eye	Postop Day 1 Fellow Eye	Postop Week 1 Fellow Eye	Postop Week 3 [REDACTED] Treatment (Bilateral)	Adjustment #1 (Bilateral)	Adjustment #2 (Bilateral)	Adjustment #3 (if needed) (Bilateral)	Lock-in #1 Primary Eye	Lock-in #2 Primary Eye, if needed	Lock-in #1 Fellow Eye	Lock-in #2 Fellow Eye, if needed	Postop Month 3 (Bilateral)	Postop Month 6 (Bilateral)	Postop Month 12 (if needed)	Unscheduled Visit 
Distance Corrected Contrast Sensitivity (Mesopic/Photopic w and w/o glare)																	M		
Intraocular Pressure	X	X	X	X	X	X	X	X	X	X	X	X	X	X	X	X 	X 	X 	
Slit Lamp Exam	X	X	X	X	X	X	X	X	X	X	X	X	X	X	X	X	X	X	
Fundus Exam	X							X								X	X		
Fundus Photos	X						X									X	X		
Spectral Domain Optical Coherence Tomography (SD-OCT)							X	X 	X 	X 	X 	X 	X 	X 	X 	X 	X 		
IOL Stability (Tilt/Decentration)								X								X	X		
Dilated Pupil Diameter	X							X	X	X	X	X	X	X					
Adverse Events		X	X	X	X	X	X	X	X	X	X	X	X	X	X	X	X	X	

 Tests indicated with an "X" must be performed at each unscheduled visit. Other tests may be conducted based on the investigator's assessment of the subject.

 Required at any unscheduled visit before the final lock-in light treatment

 Also performed on the primary eye to confirm that there has been no ultraviolet (UV) retinal damage per Section 7.3.2 before proceeding with lock-in #1 treatment on the fellow eye

M Measurements will be conducted by a masked observer who will not be aware of which lens has been implanted. The masked observer should not have access to the subject's medical and/or study records. The masked observer should not conduct any study examinations at follow-ups with masked examinations beyond the visual measurements indicated with the "M."

**Table 2. Schedule of Visits and Clinical Parameters- Control Group**

Visits	Preop (Bilateral)	Operative Primary Eye	Postop Day 1 Primary Eye	Postop Week 1 Primary Eye	Operative Fellow Eye	Postop Day 1 Fellow Eye	Postop Week 1 Fellow Eye	Postop Week 3 (Bilateral)	Postop Month 3 (Bilateral)	Postop Month 6 (Bilateral)	Unscheduled Visit 
Monocular photopic uncorrected distance visual acuity using a +0.25 D lens to compensate for 4 meter test distance	X		X	X		X	X	X	X	M	X
Binocular photopic uncorrected distance visual acuity using a +0.25 D lens over each eye to compensate for 4 meter test distance										M	
Manifest Refraction	X			X			X	X	X	M	X
Monocular photopic distance corrected visual acuity (Distance)	X			X			X	X	X	M	X
Monocular photopic uncorrected distance visual acuity (no trial lens in front of eye)	X			X			X	X	X	M	X
Ocular Dominance	X							X		M	
Undilated pupil diameter										M	
Depth of focus testing										M	
Monocular mesopic distance corrected intermediate visual acuity										M	
Monocular mesopic best corrected intermediate visual acuity										M	
Monocular mesopic best corrected near visual acuity										M	
Monocular mesopic distance corrected near visual acuity										M	
Monocular photopic distance corrected near visual acuity								X	M		
Monocular photopic uncorrected near visual acuity								X	M		
Binocular photopic uncorrected near visual acuity									M		

 Tests indicated with an “X” must be performed at each unscheduled visit. Other tests may be conducted based on the investigator’s assessment of the subject.

M Measurements will be conducted by a masked observer who will not be aware of which lens has been implanted. The masked observer should not have access to the subject’s medical and/or study records. The masked observer should not conduct any study examinations at follow-ups with masked examinations beyond the visual measurements indicated with the “M”.

## 7.7 DATA REPORTING

Electronic data capture (EDC) will be utilized for this study. Case report forms (CRFs) will be developed by the sponsor. In order to facilitate data entry, the CRFs coincide with the data entry pages in the EDC system. Research sites will be provided with source document templates (SDTs) that correlate with the CRFs. The appropriate SDTs will be completed and initialed or signed where indicated at each examination. All SDTs will be completed in a legible manner in black/blue ink.

Any corrections to the SDTs will be made by drawing a single line through the incorrect entry, recording the correct information, and initialing and dating the change. The study SDTs and data entered in the EDC system will be reviewed by the Study Monitor.

All clinical data generated in the study will be submitted to the RxSight Clinical Affairs Department or designated CRO for quality assurance review and statistical analysis. All SDTs and data entered into the EDC system will be reviewed for completeness and evident recording errors will be rectified by contact with the appropriate clinical site. Computerized data checks will be used to identify unusual data entries for verification prior to statistical analysis.

To minimize the amount of missing data, investigators will be trained on the deleterious effect that missing data have on trial integrity and credibility and that missing data could diminish the scientific value of all subjects' altruistic contributions.

## 7.8 STUDY COMPLETION PROCEDURES

An End of Study Form must be completed for all subjects enrolled in the study upon subject completion, withdrawal or discontinuation.

### 7.8.1 SUBJECT COMPLETION

For subjects with both eyes successfully implanted with a study IOL, study completion is when both the primary and fellow study eyes have completed the Postop Month 6 examination. For subjects with only the primary eye successfully implanted with a study IOL, study completion is when the primary study eye has completed the Postop Month 6 examination.

Subjects with ocular serious adverse events or adverse device effects that are unresolved at study exit should continue to be followed until resolution of the event or until they are stable per the investigator's evaluation.

### 7.8.2 SUBJECT WITHDRAWAL PRIOR TO IMPLANTATION

Subjects may be withdrawn from the study prior to implantation if they do not meet all inclusion/exclusion criteria (screen failures) or decide not to participate in the study.

### **7.8.3 SUBJECT WITHDRAWAL DUE TO INTRAOPERATIVE COMPLICATIONS PRIOR TO OR DURING ATTEMPTED IMPLANTATION**

Subjects that meet all inclusion/exclusion criteria but do not undergo implantation of the primary eye due to intraoperative complications prior to or during introduction of the IOL will be followed to stability or resolution of any adverse events and then exited from the study.

### **7.8.4 SUBJECT DISCONTINUATION AFTER IMPLANTATION**

After successful IOL implantation bilaterally or only in the primary eye, the subject will be withdrawn from the study if both IOLs are explanted or the IOL is explanted from the primary eye respectively or the subject has deceased.

The reason for discontinuation will be recorded on the appropriate study worksheet. Subjects who are discontinued from the study will still be a part of the study analyses up until the point they are exited. In the case of an explant, the investigator should continue follow-up for a period that ensures no adverse consequences have resulted. When possible, all necessary clinical assessments will be performed prior to the Subject exiting the study even if the assessment was not scheduled at that particular visit.

### **7.8.5 LOST TO FOLLOW-UP**

Subjects for which the final post-operative case report form is overdue and who refuse to be followed, or have difficulty being followed, or cannot be contacted despite extensive written and telephone follow-ups to determine the final clinical outcome, will be considered lost to follow-up. Sites must make a minimum of three documented attempts via telephone, email, or regular mail to contact the subject. If the subject does not reply to any of these attempts, the site must send a letter by certified mail (with a request for notification of receipt of delivery) to the subject. If a subject is non-responsive to these follow-up attempts, the subject will be considered to be lost to follow-up.

### **7.8.6 STUDY TERMINATION**

The study may be stopped at any time by the Sponsor for reasonable cause with appropriate notification. Conditions that may warrant study termination include, but are not limited to the following:

- Safety concerns. Clinical data from the study will be monitored to assure the safety of enrolled subjects.

If the clinical study is prematurely terminated, the Sponsor will inform the Investigator, the IRB, and other appropriate regulatory bodies. If the Sponsor terminates the study for safety reasons, it will immediately notify the Investigator, the IRB, and other appropriate regulatory bodies and provide an explanation of the reasons for termination. The Investigator will be provided with instructions for study termination and applicable subject follow-up. The Sponsor will continue to provide resources to fulfill the Clinical Study Plan obligations for follow-up of the subjects enrolled in the study.

## 8 STATISTICAL METHODS

### 8.1 SAMPLE SIZE CALCULATION

Subjects that meet all inclusion/exclusion criteria will be randomly assigned in a 1:1 ratio to either the LAL group or the Control group.

#### 8.1.1 SAMPLE SIZE FOR THE EFFECTIVENESS ENDPOINTS

##### **Primary Effectiveness Endpoints**

The first co-primary effectiveness endpoint is the change in DOF measured at the 0.20 logMAR at Postop Month 6. It is to show that the DOF of the primary eyes in the LAL group at Postop Month 6 is at least 0.5 D greater than that of the primary eyes in the Control group. The DOF will be determined based on the defocus curve of visual acuity (plot of mean logMAR visual acuity versus corresponding lens diopter) measured during the depth of focus test at Postop Month 6 for the LAL and Control groups, separately. No formal statistical test will be performed for this endpoint.

[figure not shown]
The second co-primary effectiveness endpoint is the monocular photopic DCIVA at 67 cm at Postop Month 6.

The third co-primary effectiveness endpoint is the outcome of monocular photopic DCIVA better than or equal to logMAR 0.20 for the LAL group at Postop Month 6.

The fourth co-primary effectiveness endpoint is the monocular photopic BCDVA at Postop Month 6. The clinical objective is to demonstrate that the mean monocular photopic BCDVA at Postop Month 6 for the LAL primary eyes is not inferior to that of the Control primary eyes

[REDACTED]

[REDACTED]

### **Secondary Effectiveness Endpoints**

[REDACTED]

The first secondary effectiveness endpoint is the monocular photopic DCNVA at Postop Month 6.

[REDACTED]

The second secondary effectiveness endpoint is the outcome of monocular photopic DCNVA better than or equal to 0.20 logMAR for the LAL group at Postop Month 6.

[REDACTED]

[REDACTED]

II

III

The fifth secondary effectiveness endpoint is the monocular photopic UCDVA using a +0.25 D lens at Postop Month 6. [REDACTED]

A large black rectangular redaction box covers the bottom portion of the page content, starting below the main text and ending at the bottom of the page. It is positioned to the left of the page number.

### **Sample Size for the Effectiveness Endpoints**

Based on the sample sizes discussed above for the primary and secondary effectiveness endpoints, a sample size of at least **180** ( $90 \times 2$ ) enrolled, randomized, and bilaterally treated subjects are needed for the effectiveness evaluation.

#### **8.1.2 SAMPLE SIZE FOR THE SAFETY ENDPOINTS**

##### **Primary Safety Endpoint**

The sample size for the incidence of ocular serious adverse events, including persistent and cumulative events defined per ISO 11979-7, is based on the recommendation from American Academy of Ophthalmology Task Force Consensus Statement for Extended Depth of Focus Intraocular Lenses, “*The EDF IOL group should consist of a minimum of 100 patients.*” With 100 LAL subjects, the study has 95% confidence to observe at least one incidence of safety events with a rate of at least 2.7%. With a drop-out rate of 10%, at least **112** LAL subjects with implantation attempted are needed. For comparison, at least 112 Control subjects with implantation attempted are needed.

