#### **8.1.3 SAMPLE SIZE FOR THE STUDY**

Based on Sections 8.1.1 and 8.1.2, the planned study sample size of up to 230 ( $\sim 112 \times 2$ ) enrolled and randomized subjects who have had LAL implantation (LAL group) or Control IOL implantation (Control group) attempted is sufficient.

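### Section 8.1.2: 100 LAL subjects give a 95% chance of seeing at least one safety event at a true rate of about 2.95%, not 2.7%

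*Combined protocol and SAP*

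**What the plan says.** Section 8.1.2 sizes the study for the primary safety endpoint, the ISO 11979-7 ocular serious adverse events, both cumulative and persistent. The number 100 is taken from a cited consensus statement: "The EDF IOL group should consist of a minimum of 100 patients". The plan then says what that number can detect: "With 100 LAL subjects, the study has 95% confidence to observe at least one incidence of safety events with a rate of at least 2.7" percent. The next step begins "With a drop-out rate of 10" percent and raises 100 to 112 LAL subjects with implantation attempted. The Control group is set to match: "For comparison, at least 112 Control subjects with implantation attempted are needed". Section 8.1.3 then describes up to 230 "enrolled and randomized subjects who have had LAL implantation (LAL group) or Control IOL implantation (Control group) attempted is sufficient".

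Three other places matter. Section 8.3.2 defines the modified safety population as subjects with implantation attempted, uses it for the safety summaries and rules out imputation. Section 8.6 bases those summaries on observed data. Section 8.6.1 compares the ISO event rates at Postop Month 6 with the ISO reference rates through a one-sided lower 95% confidence limit.

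**The concern.** The sentence gives a sample size, a probability and an event rate. Any two of these fix the third, so it can be checked without outside information, and the rate does not follow from the other two.

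It is the only detection figure offered for the primary safety endpoint, and it errs in the flattering direction: it says that 100 subjects can reveal a rarer event than they can at the stated probability. Because the next step inflates 100 to 112 for drop-out, the text presents 100 as the number left after losses. That is roughly the number to be expected for persistent events at Month 6, so a reader could reasonably carry 2.7% over to those events.

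**Working it through.** **Inputs, all from Section 8.1.2 unless noted**

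- LAL subjects: n = 100
- Probability of at least one event: 95%
- Stated event rate: 2.7%
- Drop-out: 10%, giving 112 LAL subjects with implantation attempted
- Study total: up to 230, or 115 per group if split equally (Section 8.1.3)

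**Formula.** With independent subjects and a true rate p, P(at least one event) = 1-(1-p)^n. Setting this to 0.95 gives p = 1-0.05^(1/n).

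**Attempt to reproduce the plan's figure at n = 100**

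- Rate for 95%: 1-0.05^(1/100) = 0.0295, or 2.95%
- Probability at 2.7%: 1-0.973^100 = 0.9352, or 93.5%
- Subjects needed for 95% at 2.7%: ln(0.05)/ln(0.973) = 109.4, so 110 (109 gives 94.94%, 110 gives 95.07%)

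**Other readings that might give 2.7%**

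| Reading | Detectable rate |
|---|---|
| n = 100, Poisson, -ln(0.05)/100 | 3.00% |
| n = 100, rule of three, 3/100 | 3.00% |
| n = 100, 90% probability | 2.28% |
| n = 100, 97.5% probability | 3.62% |
| 200 eyes instead of 100 subjects | 1.49% |
| 90 subjects (100 less 10%) | 3.27% |

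None gives 2.7%. Rounding does not explain it either, since 2.95% rounds to 3.0%.

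**Where 2.7% does fit**

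| n | Rate for 95% (exact) | Probability at 2.7% |
|---|---|---|
| 100 | 2.95% | 93.5% |
| 110 | 2.69% | 95.1% |
| 112 | 2.64% | 95.3% |
| 115 | 2.57% | 95.7% |

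At n = 112 the rule of three gives 3/112 = 2.68%. The figure may therefore have been worked out at the inflated number and then attached to 100. That is a guess; the plan does not say so.

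**Drop-out step.** 100/0.9 = 111.1, rounded up to 112, which agrees with the plan. In reverse, 112 x 0.9 = 100.8, so about 100 LAL subjects are expected to have Month 6 data if recruitment stops at the minimum and the full 10% is lost.

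**The case against.** The strongest reply is that nothing rests on the figure. The 100 comes from the consensus recommendation, the 112 from the drop-out allowance, the total of 230 from those, and the ISO comparison in Section 8.6.1 never uses 2.7%. This is correct, and it limits the point to a wrong statement rather than a weak design.

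Second, the plan achieves 2.7% over its own safety population, because Section 8.3.2 counts everyone with implantation attempted and at least 112 such LAL subjects are planned. This also stands for events counted over all of those subjects. It does not rescue the sentence, which names 100.

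Third, the link to Month 6 persistent events is an inference. Section 8.1.2 speaks of safety events in general, and Section 8.6.1 states no separate Month 6 denominator. The expected number also depends on recruitment and losses: with 115 LAL subjects and 10% drop-out, 115 x 0.9 = 103.5 remain and the rate is 1-0.05^(1/103.5) = 2.85%. This is fair. The observed-data rule in Section 8.6 and the ban on imputation in Section 8.3.2 make a denominator near 100 plausible without fixing it. The mismatch within the sentence does not depend on that inference.

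Last, 93.5% against 95% is a small gap. It is, but the sentence fixes 95% and reports the rate as its result, so the rate is the figure to correct.

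**Conclusion.** The concern holds. With 100 LAL subjects the rate detectable with 95% probability is 2.95%, not 2.7%; at 2.7% the probability is 93.5%. The size is 0.25 percentage points in the rate, 1.5 points in the probability, or 10 subjects (110 against 100). There is no shortfall for events counted over all 112 or more LAL subjects with implantation attempted.

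The calculation assumes one independent outcome per subject and a common true rate. The Month 6 reading further assumes recruitment at the minimum of 112 and the full 10% drop-out. The sentence should be corrected because it is the plan's stated detection figure for the primary safety endpoint and is untrue for the number it names; the adequacy of the sample size is not in question.

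**What to change.** Change the sentence in Section 8.1.2 in one of two ways.

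1. Keep 100 subjects and give the detectable rate as at least 3.0% (2.95%). At 3.0% the probability is 1-0.97^100 = 95.2%.
2. Keep 2.7% and attach it to the 112 LAL subjects with implantation attempted, adding that the figure is about 3.0% for events assessed only in the roughly 100 subjects expected to have Month 6 data.

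The first is simpler and needs no assumption about the Month 6 denominator. Either costs one figure or one clause. Enrolment, analysis populations, endpoints and the ISO comparison stay as they are.

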#### **8.1.3 SAMPLE SIZE FOR THE STUDY**

Based on Sections 8.1.1 and 8.1.2, the planned study sample size of up to 230 ( $\sim 112 \times 2$ ) enrolled and randomized subjects who have had LAL implantation (LAL group) or Control IOL implantation (Control group) attempted is sufficient.

### **8.2 GENERAL CONSIDERATION**

The statistical analysis of the data will be performed using SAS version 9.3 or higher or another industry standard statistical software package. Continuous variables will be summarized using descriptive statistics, specifically the mean, median, standard deviation, minimum and maximum. Categorical variables will be summarized by frequencies and percentages. For monocular measurements such as refraction or monocular visual acuity, the summaries will be provided for the primary eyes and fellow eyes of the LAL subjects and those of the Control subjects separately. For binocular measurements such as binocular visual acuity or the patient reported outcomes, the summaries will be provided for the LAL subjects and Control subjects separately. The 95% confidence interval for mean or for percentage may be provided.

Unless otherwise specified, all p-values will be two-sided for a two-sided significance level of 0.05 or one-sided for a one-sided significance level of 0.025. In general, the confidence intervals will be two-sided at 95% confidence level. For the ISO-specified cumulative or persistent adverse event rate, one-sided lower 95% confidence limit will be provided.

### **8.3 POPULATIONS FOR ANALYSIS**

#### **8.3.1 PRE-COVID-19 POPULATION**

The Pre-COVID-19 population consists of any subject (or eye) who has signed the informed consent and has had the LAL or Control lens implantation attempted, which is defined as the point at which the lens makes contact with the eye, prior to the March, 2020 suspension of cataract surgeries. Safety and effectiveness analyses for subjects in this population will be

performed separately. Seventeen subjects (10 LAL and 7 Control) met this definition. Due to the COVID-19 pandemic, study visits for these 17 subjects may have been delayed outside protocol specified windows or missed completely. Therefore these subjects will be excluded from the modified safety and Full Analysis Set populations.

